#### 7.5.6. Mean low AC dB hearing threshold (AC over 0.25, 0.5, 1, and 2 kHz)

- *Computation of the Endpoint*

At each visit and by ear (left, right), the mean low AC dB hearing threshold will be derived by averaging the AC audiometry dB hearing thresholds over 0.25, 0.5, 1, and 2 kHz frequencies. Left and right ears will be mapped to treated and untreated for analysis, as described in Section 3. Missing values will be imputed per Section 7.5.

- *Analysis of the Endpoint*

The mean low AC dB hearing threshold will be summarized descriptively for subjects in the FAS as described in Section 7.5.5. Treatment group comparisons will also be performed as described in Section 7.5.5.

- *Sensitivity Analyses of the Endpoint*

The analyses will be repeated for subjects in the PPAS.

If there are any dosing administrations errors such that a not qualified ear is treated, the descriptive summaries by treated and untreated ears will be repeated for subjects in the FAS including all treated and untreated ear data.

#### 7.5.7. Mean high AC dB hearing threshold (AC over 3, 4, 6 and 8 kHz)

- *Computation of the Endpoint*

At each visit and by ear (left, right), the mean high AC dB hearing threshold will be derived by averaging the AC audiometry dB hearing thresholds over 3, 4, 6 and 8 kHz frequencies. Left and right ears will be mapped to treated and untreated for analysis, as described in Section 3. Missing values will be imputed per Section 7.5.

- *Analysis of the Endpoint*

The mean high AC dB hearing threshold will be summarized descriptively for subjects in the FAS as described in Section 7.5.5. Treatment group comparisons will also be performed as described in Section 7.5.5.

- *Sensitivity Analyses of the Endpoint*

The analyses will be repeated for subjects in the PPAS.

If there are any dosing administrations errors such that a not qualified ear is treated, the descriptive summaries by treated and untreated ears will be repeated for subjects in the FAS including all treated and untreated ear data.

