#### 7.5. Pure Tone Audiometry

The pure tone audiometry test will be used to determine a subject's threshold for hearing at the following frequencies transmitted via air and bone: air tested at 0.25, 0.5, 1, 2, 3, 4, 6 and 8 kHz; and bone tested at 0.5, 1, 2, 3 and 4 kHz. If both masked and unmasked results are available for the same visit, date, ear, and frequency, the masked results will be used for analysis. This test will be performed at Screening, Day 15, 60, 90, 150, and 210.

Baseline scores for analysis will be computed from the Screening visit. For measurements post-Screening, missing response values for a given frequency, with classification of "NR" (no response due to subject audiometric thresholds greater than the maximal calibrated dB of the equipment), will be imputed using the maximum dB for the audiometry equipment of a given site plus 5 dB and classified as no signal at that frequency. Missing response values at Screening will remain missing.

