#### 7.5.5. Mean overall PTA (AC over 0.5, 1, 2, and 4 kHz) and BCA (BC over 0.5, 1, 2 and 4 kHz)

- *Computation of the Endpoint*

At each visit and by ear (left, right), the mean overall PTA will be derived by averaging the AC audiometry dB hearing thresholds over 0.5, 1, 2, and 4 kHz frequencies. Left and right ears will be mapped to treated and untreated for analysis, as described in Section 3. Missing values will be imputed per Section 7.5. The BCA will be derived using the same approach. If hearing thresholds are missing for any of the 0.5, 1, 2, and 4 kHz frequencies (after imputation of records with classification of "NR"), PTA or BCA will be missing, respectively.

Mean overall PTA for each ear will be categorized into  $<26$ , 26-40, 41-55, 56-70, and  $>70$  for each visit and shifts from baseline to each post-baseline visit will be computed (e.g., 26-40 to 41-55).

- *Analysis of the Endpoint*

The mean overall PTA will be summarized descriptively for treated ears separately by visit and treatment group for subjects in the FAS. The summary will be repeated for BCA.

In treated ears only for subjects in the FAS, treatment group comparisons for mean overall PTA will be analyzed using a mixed-effect, repeated measures model using fixed covariates for treatment group, WR score at baseline ( $<50\%$  versus  $\geq 50\%$ ), etiology of hearing loss

(SSNHL versus NIHL), visit, and interaction between visit and treatment group. As described in Section 7.3.4, separate models will be fit specifying UN and AR(1) covariance structures (implemented with a repeated statement in SAS). The covariance structure providing the lowest corrected AICc and BIC values from the model will be implemented for the PTA and all other audiometry endpoints. The treatment group differences analyzed will be between each FX-322 group (including the pooled FX-322 group) versus placebo, and comparisons between the individual FX-322 groups (excluding the pooled FX-322 group). Comparisons will be made by visit (e.g., estimated LS Mean differences by visit) and overall (e.g., Type III Sums of Squares). The treatment group comparisons will also be performed for BCA.

The distribution in the shift in mean overall PTA categories for treated ears from baseline to each post-baseline visit will be summarized using frequencies and percentages by visit and treatment group for subjects in the FAS.

- *Sensitivity Analyses of the Endpoint*

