#### 7.6.5. Mean dB hearing threshold (AC over 9-16 kHz)

- *Computation of the Endpoint*

At each visit and by ear (left, right), the mean dB hearing threshold will be derived by averaging the AC audiometry dB hearing thresholds over 9-16 kHz frequencies. Left and right ears will be mapped to treated and untreated for analysis, as described in Section 3. Missing values will be imputed per Section 7.6.

- *Analysis of the Endpoint*

Descriptive summaries and treatment group comparisons will be performed for mean dB hearing threshold as described in Section 7.5.5.

- *Sensitivity Analyses of the Endpoint*

The analyses will be repeated for subjects in the PPAS.

If there are any dosing administrations errors such that a not qualified ear is treated, the descriptive summaries by treated and untreated ears will be repeated for subjects in the FAS including all treated and untreated ear data.

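### NR is coded after Screening but left missing at Screening, and the high and 9-16 kHz averages have no incomplete-set rule, so their Screening and follow-up means are not comparable

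*SAP*

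**What the plan says.** **NR coding.** Under SAP 7.5, an NR frequency after Screening is "imputed using the maximum dB for the audiometry equipment of a given site plus 5 dB" and classed as no signal. For the baseline visit the rule differs: "Missing response values at Screening will remain missing". SAP 7.6 repeats both rules for extended high frequency audiometry.

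**Averages with an incomplete-set rule.** SAP 7.5.5 covers PTA and BCA: "If hearing thresholds are missing for any of the 0.5, 1, 2, and 4 kHz frequencies" once NR has been imputed, the average is itself missing.

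**Averages without one.** The mean high threshold (7.5.7) is "derived by averaging the AC audiometry dB hearing thresholds over 3, 4, 6 and 8 kHz frequencies", the mean low threshold (7.5.6) is "derived by averaging the AC audiometry dB hearing thresholds over 0.25, 0.5, 1, and 2 kHz frequencies", and the extended average (7.6.5) is "derived by averaging the AC audiometry dB hearing thresholds over 9-16 kHz frequencies". Each adds only that missing values are imputed under 7.5 or 7.6. Their references to 7.5.5 stand under the analysis of the endpoint, not its computation, so they do not clearly bring the missing-data rule with them.

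**Use.** These averages are summarised by visit and modelled as levels, with the 7.5.5 covariates (treatment, word recognition stratum, etiology, visit, visit by treatment). Protocol 7.2 states the audiometry endpoints as mean changes from Screening.

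**The concern.** NR at Screening is to be expected at the high frequencies. Protocol 8.4.2 limits only the study ear's average over 0.5, 1, 2 and 4 kHz; nothing limits 6, 8 or 9-16 kHz. SAP 7.6.6 to 7.6.8 define endpoints for ears with no signal at baseline at one, two or three contiguous extended frequencies, so half of the six components of the 9-16 kHz average may be absent at Screening.

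Such an ear has a numerical value at those frequencies at every later visit but none at Screening. A table of means by visit can then show a change in hearing that comes only from coding. An ear that regains a response, which is the result the trial hopes for, can appear worse than at Screening.

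**Working it through.** The plan states no figure on this point, so there is none to reproduce.

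**Inputs from the documents.** m = 4 frequencies (high average) or 6 (9-16 kHz); NR after Screening = M + 5 dB, with M the site's equipment maximum; NR at Screening = missing.

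**Inputs assumed.** M and all thresholds. The documents give neither, so they are varied below.

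**Reading A: available values are averaged.** Take an unchanged ear with k of m frequencies NR at both visits and mean s over the measured ones.

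- Screening mean = s
- Follow-up mean = [(m − k)s + k(M + 5)]/m
- Shift = (k/m) × [(M + 5) − s]

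For 3/4/6/8 kHz = 65/75/90/NR and M = 100:

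- Screening: (65 + 75 + 90)/3 = 76.7 dB
- Follow-up: (65 + 75 + 90 + 105)/4 = 83.75 dB
- Shift: (1/4) × (105 − 76.7) = +7.1 dB, with hearing unchanged

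If 8 kHz recovers to 95 dB, the mean is (65 + 75 + 90 + 95)/4 = 81.25 dB. That is 4.6 dB worse than Screening, although it is 2.5 dB better than the 83.75 dB the ear would have had with NR.

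Range under other assumptions:

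| Average | Measured (dB) | NR | M (dB) | Shift (dB) |
|---|---|---|---|---|
| High | 75/80/85 | 1 of 4 | 90 | (95 − 80)/4 = +3.75 |
| High | 60/65/70 | 1 of 4 | 80 to 110 | +5.0 to +12.5 |
| High | 40/50/60 | 1 of 4 | 110 | (115 − 50)/4 = +16.25 |
| High | 65/75 | 2 of 4 | 80 to 110 | +7.5 to +22.5 |
| 9-16 kHz | 50/60/65/70 | 2 of 6 | 85 | (90 − 61.25)/3 = +9.6 |
| 9-16 kHz | 70/75/80/80 | 2 of 6 | 60 at the NR frequencies | (65 − 76.25)/3 = −3.75 |

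The last row shows that the sign is not fixed. If the maximum is frequency-specific and M + 5 lies below the measured mean, the artefact is a false gain.

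**Reading B: incomplete sets are set to missing.** There is no within-ear shift, but the ears behind each visit's mean differ. Take two unchanged ears, A = 50/55/60/65 and B = 65/75/90/NR, with M = 100:

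- Screening: A only, 57.5 dB
- Follow-up: (57.5 + 83.75)/2 = 70.6 dB
- Displayed difference: +13.1 dB

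B's change from Screening cannot be computed.

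**A frequency not done at follow-up (Reading A).** SAP 7.1.6 recognises this category, and it is not imputed at any visit. In the 65/75/90/NR ear, omitting 3 kHz gives (75 + 90 + 105)/3 = 90.0 instead of 83.75 dB. In an unchanged 60/65/70/85 ear, omitting 8 kHz gives 65.0 instead of 70.0 dB. Either value enters the model outcome directly.

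**NR coded alike at both visits.** The example ear has 83.75 dB at Screening and at follow-up: shift 0 dB. In Reading B's example both visits average 70.6 dB.

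**The case against.** The strongest reply is that the SAP nowhere says available values are averaged. A mean over four named frequencies can be read as needing all four, and the SAP mostly requires complete data elsewhere: WR and WIN are not scored if incomplete (7.3, 7.4), and HHIA and HSI are missing if any item is (7.8, 7.9). Where it wants an available-item mean, as for the TFI (14.3), it says so. This stands: different frequency sets cannot be presented as what the SAP specifies. It does not rescue the by-visit summaries, because Reading B leaves different ears at Screening and follow-up.

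The second reply is that treatment comparisons are hardly touched. No change-from-baseline version of these averages is defined, the model has no threshold covariate, and NR coding is the same at all later visits. Randomisation should balance Screening NR on average, though chance imbalance is possible at 24 per arm. This stands too, with two exceptions: a frequency not done at follow-up under Reading A, and Screening being fitted as a model visit, which the SAP does not settle.

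Third, the per-frequency summaries (7.5.1, 7.6.1) and the accountability table (7.1.6) would let a careful reader notice a changing frequency set. That mitigates the problem without removing it. There is also no single primary endpoint, p-values are descriptive, and extended high frequency audiometry is an additional exploratory endpoint.

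**Conclusion.** The point holds as a comparability defect in the high and 9-16 kHz averages. Its main cause is the unequal NR coding in 7.5 and 7.6; the unstated incomplete-set rule decides only which form it takes. Under available-value averaging and the assumed limits, an affected ear typically shows several dB of false loss (7.1 dB in the worked example). The harm is confined to summaries read against Screening and to the protocol's change-from-Screening endpoints.

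A reader might infer more, and the documents do not support it:

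- **A fixed false loss of about 5 dB.** No equipment limit, threshold or NR rate is given. With one NR of four, 5 dB requires M + 5 to exceed the measured mean by exactly 20 dB. Size and sign both depend on assumptions.
- **A bias in the treatment effect.** Contrasts after Screening are largely unaffected, apart from the two exceptions above.
- **Equal exposure of the low average.** The entry limit makes NR at 0.5, 1 or 2 kHz unlikely in the study ear, so 7.5.6 shares the wording gap but little of the effect.

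**What to change.** Make two changes together.

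1. In SAP 7.5 and 7.6, code NR at Screening as at later visits (site maximum plus 5 dB, flagged as no signal), for the individual frequencies as well as the averages. Keep a frequency that was not tested as missing.
2. In 7.5.6, 7.5.7 and 7.6.5, add the 7.5.5 rule under the computation: the average is missing unless every component has a value after NR coding.

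The second change alone would drop the Screening mean of every ear with a Screening NR in that average. Recoding only inside the averages would leave the same frequency missing in 7.5.1 or 7.6.1 but present in the mean.

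It would also help to state whether Screening is a visit in the model.

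The cost is SAP wording and the matching derivation. A few averages become missing where a frequency was not tested. Other endpoints that use the individual thresholds would gain a Screening value at NR frequencies, so their derivations should be checked against the new rule.

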#### 7.5.8. Air-Bone Imbalance at 0.5, 1, 2, 3, and 4 kHz

- *Computation of the Endpoint*

At each visit and by ear (left, right), Air-Bone imbalance is computed as AC-BC dB hearing thresholds at 0.5, 1, 2, 3, and 4 kHz. Left and right ears will be mapped to treated and untreated for analysis, as described in Section 3. Missing threshold values will be imputed per Section 7.5 prior to the derivation.

Air-bone imbalance at each frequency will be categorized into  $\leq 10$  dB versus  $> 10$  dB for each visit and shifts from baseline to each post-baseline visit will be computed (e.g.,  $\leq 10$  dB to  $> 10$  dB).

- *Analysis of the Endpoint*

The Air-Bone imbalance at each frequency (0.5, 1, 2, 3, and 4 kHz) will be summarized descriptively for treated ears by visit and treatment group for subjects in the FAS.

The distribution in the shift in air-bone imbalance for treated ears at each frequency from baseline to each post-baseline visit will be summarized using frequencies and percentages by visit and treatment group for subjects in the FAS.

- *Sensitivity Analyses of the Endpoint*

The analyses will be repeated for subjects in the PPAS.

If there are any dosing administrations errors such that a not qualified ear is treated, the descriptive summaries by treated and untreated ears will be repeated for subjects in the FAS including all treated and untreated ear data.

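### SAP 7.5.8 subtracts bone from air conduction after filling no-response values with an equipment limit, so those air-bone gaps are bounds or equipment constants reported as measurements

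*SAP*

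**What the plan says.** SAP 7.5.8 defines the quantity by ear and visit: "Air-Bone imbalance is computed as AC-BC dB hearing thresholds at 0.5, 1, 2, 3, and 4 kHz". It fixes the order of operations: "Missing threshold values will be imputed per Section 7.5 prior to the derivation". Each gap is then classed as ≤10 dB or >10 dB, and "shifts from baseline to each post-baseline visit will be computed". The gap itself "will be summarized descriptively for treated ears by visit and treatment group for subjects in the FAS". No model or test is attached.

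SAP 7.5 supplies the imputation. A post-Screening value recorded as NR "will be imputed using the maximum dB for the audiometry equipment of a given site plus 5 dB". The section explains NR as a threshold beyond what the equipment can present. It does not say whether air and bone have separate maxima, or whether the maximum varies by frequency. Baseline is treated differently: "Missing response values at Screening will remain missing".

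Nothing in 7.5.8 flags, bounds or excludes a gap in which one or both thresholds were imputed.

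**The concern.** By the SAP's own definition, NR says only that a threshold lies above a limit. Adding 5 dB to that limit gives a workable stand-in for one threshold. Subtracting one stand-in from another, or from a measured value, gives a number that depends on the audiometer as well as the ear. When both thresholds are NR it depends on the audiometer alone.

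The direction of the error turns on a point that SAP 7.5 leaves open. Two programmers following the same text could put the same ear in opposite classes.

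This matters because Protocol 6.2 names both conductive and sensorineural loss among the injection risks, every subject receives four injections (Protocol 8.7.3), and 7.5.8 is the only planned output that computes the air-bone gap within an ear. The pure tone results are also in the Day 90 interim package (SAP 10).

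**Working it through.** The documents give no figure to reproduce here, so the check applies the SAP rule directly.

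**Inputs.** The rule, the order of operations and the 10 dB cut come from SAP 7.5 and 7.5.8. Equipment limits are not in the documents. Assumed: air limit L_A from 90 to 120 dB and bone limit L_B from 50 to 80 dB, or L_B equal to L_A, with thresholds in 5 dB steps. AC and BC are the air and bone thresholds.

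**Reading A: one maximum M for air and bone (the literal wording), with M = L_A.**
- Both NR: (M + 5) - (M + 5) = 0 dB whatever the true gap, so always ≤10 dB.
- BC NR, AC measured: AC is at most M, so AC - (M + 5) is at most -5 dB, always ≤10 dB.
- When does the second case hide a real gap? BC NR means a true BC of at least L_B + 5, so the true gap is at most M - L_B - 5. That exceeds 10 dB only if M - L_B is more than 15 dB. If bone can be tested up to M, the ≤10 dB class is correct.
- Example, M = 110 and L_B = 60: true AC 90 and BC 65, gap 25 dB. Recorded: 90 - 115 = -25 dB.

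**Reading B: separate maxima.**
- Both NR: (L_A + 5) - (L_B + 5) = L_A - L_B, a constant. At 110/70 it is 40 dB. Over the assumed limits it runs from 90 - 80 = 10 to 120 - 50 = 70 dB. It is >10 dB unless the limits are within 10 dB of each other, even for a purely sensorineural ear.
- BC NR, AC measured: AC - (L_B + 5) is an upper bound on the true gap. No true gap is missed, but false ones can appear. At 110/70, true AC 100 and BC 95 (gap 5 dB) is recorded as 100 - 75 = 25 dB.

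**AC NR, BC measured (either reading).** The recorded value, L_A + 5 - BC, is a lower bound. If L_A is at least 10 dB above L_B, then BC is at most L_A - 10 and the recorded value is at least 15 dB, correctly >10 dB. If the limits coincide, it can be as low as 5 dB.

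| Post-Screening pair | One maximum | Separate maxima |
|---|---|---|
| Both NR | 0 dB | L_A - L_B, constant |
| BC NR only | at most -5 dB | upper bound |
| AC NR only | lower bound | lower bound |

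**Which outputs are affected.** Screening NR stays missing, so those ears have no baseline class. The shift table is distorted only for ears measured at Screening and NR later. The by-visit summaries also take in ears already NR at Screening: absent at baseline, then given a value at every follow-up visit without any change in hearing. With M = 110, one such ear with stable AC of 85 and BC NR enters at 85 - 115 = -30 dB. In a group of 24 whose other 23 ears have a gap of 0, the mean becomes -30/24 = -1.25 dB.

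**Can NR occur?** Protocol 8.4.2 admits a four-frequency average up to 70 dB. Thresholds of 50, 60, 70 and 100 dB average 280/4 = 70 dB, so bone NR at one frequency is plausible. This describes severity at entry. It gives no rate of NR, and none for ears that lose a bone response after Screening.

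**The case against.** The strongest reply has four parts.

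- SAP 7.5 works frequency by frequency and ties NR to the calibrated limit of the equipment, so a sensible programmer would fill bone NR with the bone limit. Reading A would then not arise, and with only bone NR no true gap would be missed.
- A purely conductive change, such as a perforation or effusion, raises the air threshold and leaves bone measurable. Bone is then not imputed, and if air becomes NR the gap is usually still >10 dB.
- Other outputs address conductive change: separate air and bone thresholds (SAP 7.5.1), otoscopy with perforation size and middle-ear findings (8.6.3), and tympanometry with shifts (8.6.4). SAP 7.1.6 tabulates NR by frequency and visit.
- The table is descriptive, and the criteria for adverse events of special interest in Protocol 13 do not use the gap.

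All of this limits the consequence and stands to that extent. It does not rescue the derivation. With both thresholds NR, the value is an equipment constant under either reading, and separate maxima exchange hidden gaps for false ones. The NR counts show how often the problem occurs but do not correct the derived gap. The other outputs give supporting evidence, but none computes the gap.

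**Conclusion.** The derivation should be changed. Followed as written, 7.5.8 reports bounds and equipment constants as measured air-bone gaps whenever a post-Screening threshold is NR. Under one maximum, every pair with bone NR is classed ≤10 dB, which hides a true gap only where one exists (with bone alone NR, this needs a bone limit more than 15 dB below the maximum). Under separate maxima, false >10 dB results can appear. The numerical examples rest on assumed limits. The number of ears affected cannot be derived from the documents.

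Three stronger readings are not supported:

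- A reader might infer that the plan would systematically hide conductive loss caused by the injections. Masking needs a bone NR filled with a higher limit, or both thresholds NR. Air NR with bone measured is normally still classed >10 dB, except where the two limits nearly coincide.
- A reader might infer that the artefact falls only on ears that worsened. That is true of the shift table. The by-visit summaries also include ears NR since Screening that did not change.
- A reader might infer that a test or safety trigger is compromised. No test is planned on this quantity, and no special-interest criterion uses it. What is affected is the interpretation of conductive change after injection.

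**What to change.** In SAP 7.5.8, replace the imputation sentence with these rules, using the maximum for the transducer and frequency concerned:

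- **Continuous summary:** exclude any air-bone pair with an NR component.
- **AC NR, BC measured:** >10 dB if AC maximum + 5 - BC exceeds 10; otherwise not evaluable.
- **AC measured, BC NR:** ≤10 dB if AC - BC maximum - 5 is 10 or less; otherwise not evaluable.
- **Both NR:** not evaluable.
- **Reporting:** give the number of not-evaluable pairs by treatment group and visit.

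In SAP 7.5, state that the NR maximum is defined by transducer and frequency. Site-specific maxima can stay, and 7.6 needs no change for this purpose because it has no bone testing.

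Checked on assumed limits: AC 90 with BC NR at a bone limit of 60 gives 90 - 65 = 25, not evaluable instead of -25 dB. AC 85 with BC NR at a bone limit of 70 gives 85 - 75 = 10, so the ear keeps its valid ≤10 dB class. AC NR at an air limit of 110 with BC 60 gives 115 - 60 = 55, so >10 dB.

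The cost is SAP wording and one derivation change. The downside is that a few ear-frequencies become not evaluable. No new data collection is needed beyond each site's equipment limits by transducer and frequency.
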